3.1 Inclusion Criteria

1. Sclerotic chronic GVHD (classic chronic or overlap syndrome) that meets 2014 NIH Consensus Criteria. Eligible patients will have superficial or deep skin sclerosis, fasciitis or joint contractures.
2. The subject must have received the following therapy for chronic GVHD (not necessarily for sclerotic manifestations):
 - a) Systemic corticosteroids for >12 months and at least one additional line of systemic therapy **OR**
 - b) Systemic corticosteroids and at least two additional lines of systemic therapy.

For the purpose of this study, intra-oral narrow-band UVB phototherapy and “FAM” (fluticasone, azithromycin and montelukast) therapy for lung GVHD will be considered a topical therapy. Investigators are encouraged but not mandated to use ibrutinib for appropriate patients prior to enrollment in this trial.

3. Adults, Age \geq 18 years (state of Nebraska, Age \geq 19 years)
4. Karnofsky performance status \geq 60% at the time of enrollment
5. All allogeneic donor sources and all conditioning regimens are allowed.
6. Absolute neutrophil count (ANC) greater than 1000/ μ L, and platelet count \geq 50,000/ μ L without the use of growth factors or platelet transfusion.
7. Able to take orally-administered medication.
8. Female patient of reproductive potential must have a negative serum or urine pregnancy test \leq 7 days prior to starting the study drug. Women are considered NOT to have reproductive potential if they have had 12 months of amenorrhea with an appropriate clinical profile (i.e. \geq 51 years, history of vasomotor symptoms, OR supportive hormone levels such as low estrogen and high follicle-stimulating hormone levels), OR surgical sterilization.
9. Male and female subjects of reproductive potential must be willing to avoid pregnancy or fathering children from enrollment to one month after the end of study treatment. This will require either a total abstinence, OR exclusively non-heterosexual activity (when this is in line with the preferred and usual lifestyle of the subject), OR two methods of contraception (male or female condom with or without a spermicidal agent, diaphragm or cervical cap with spermicide, or hormonal based contraception including intrauterine device).
10. Life expectancy greater than 6 months
11. Written informed consent to participate in the study.

3.2 Exclusion Criteria

1. Fibrosis of internal organs such as gut, liver or lung as the sole manifestation of sclerosis.
2. Fluconazole at a dose more than 200 mg daily. Subjects should stop fluconazole or lower dose to less than or equal to 200 mg daily before starting ruxolitinib.
3. Current evidence of malignancy after allogeneic transplant.
4. History of progressive multifocal leuko-encephalopathy (PML)
5. Active uncontrolled bacterial, fungal, parasitic, or viral infection. Infections are considered controlled if appropriate therapy has been instituted and, at the time of screening, no signs of infection progression are present. Progression of infection is defined as hemodynamic instability attributable to sepsis, new symptoms, worsening physical signs or radiographic findings attributable to infection. Persisting fever without other signs or symptoms will not be interpreted as progressing infection
6. Presence of known HIV infection, active hepatitis B or C infection.
7. Active tuberculosis infection that developed after allogeneic HCT
8. Total bilirubin $1.5 \times$ the upper limit of the normal range
9. Creatinine clearance <30 mL/min
10. Presence of uncontrolled cardiopulmonary conditions such as ongoing cardiac arrhythmias, unstable angina or myocardial infarction, uncontrolled hypertension (e.g. blood pressure higher than 150/90), New York Heart Association class III/IV congestive heart failure, or requirement of supplemental oxygen at rest or having a resting O₂ saturation $<90\%$ by pulse oximetry
11. Any other condition that is judged by the physician to potentially interfere with compliance to the study protocol or pose a significant risk to the patient.
12. Pregnancy, breastfeeding or planning to be pregnant.
13. Exposure to JAK inhibitor therapy for any indication after allogeneic transplant
14. Initiation of a new systemic immunosuppressant for management of chronic GVHD within 8 weeks prior to enrollment. However, subjects who develop disease progression can enroll as early as 4 weeks after initiation of a new systemic immunosuppressant. Also, subjects who are unable to tolerate current therapy can enroll any time after initiation of a new systemic immunosuppressant, as long as the “new” immunosuppressant is stopped in these cases prior to initiation of ruxolitinib. Initiation of any new topical therapy (including FAM or intra-oral narrow-band UVB phototherapy) and changes in dose of existing immunosuppressive agents such as corticosteroids, sirolimus, calcineurin inhibitors or other agents are acceptable at any time prior to enrollment. The use of immunosuppressants for short term period, for example 7 days, for indications other than GVHD will be acceptable.
15. Treatment with any other investigational agent, device, or procedure, within 21 days (or 5 half-lives, whichever is greater)
16. Known allergies, hypersensitivity, or intolerance to any of the study medications, excipients, or similar compounds.

3.3 Inclusion of Women and Minorities

Both men and women and members of all races and ethnic groups are eligible for this trial.

Section 4.0 Registration Procedure

4.1 Recruitment

Subjects who are referred to the UNMC/Nebraska Medicine or other IRB approved participating sites with sclerotic chronic GVHD may be eligible for this trial.

Screening eligibility is based on standard clinical care performed by the transplant physician. The subject's treating physician will determine eligibility based on the criteria listed in Section 3.0 prior to offering consent. All study personnel from UNMC and non-UNMC IRB approved sites will contact the UNMC IIT Office if a subject appears to meet the eligibility criteria (pending further screening tests) to confirm that target accrual has not been met.

Some insurance carriers may decline to cover the costs of usual medical care if the subject is participating in a clinical trial. The potential subject will be provided assistance by the research nurse coordinator or designated staff in determining if the insurance carrier will decline coverage. Insurance carriers may or may not pay for study related expenses. The potential subject can then decide if he/she wishes to participate.

If the subject is screened as potentially eligible, he/she will then be offered the option to participate. An informed consent will be signed by the subject after thorough review of the study is completed with the physician and his/her designee.

4.2 Eligibility Verification/Registration

Before subjects are registered into the study, the Eligibility Checklist form (Appendix F) must be completed to confirm whether the subject meets the eligibility criteria. The Eligibility Checklist form will be maintained in the study file as source documentation only if it has been reviewed, signed and dated prior to registration by the treating physician.

- Date of enrollment is defined as the date of informed consent.

All subjects will be registered through the sponsor site (UNMC). Study personnel from UNMC and non-UNMC IRB approved sites will contact the UNMC Project Coordinator if a potential subject appears to meet eligibility criteria. The site study coordinator will email the following information:

- Registration request with demographics form (located in the Study Site Manual),
- Copy of the signed/dated consent form with at least one viewable unique subject identifier,
- Completed Eligibility Checklist signed/dated by the PI or sub-I.

Once the UNMC Research Project Coordinator confirms that the subject meets criteria, and target accrual has not been met, approval for the subject will be given and study subject number assigned. The UNMC Research Project Coordinator will send a confirmation of registration

email to the site. The Project coordinator can assign a subject study number prior to final registration confirmation of a subject.

In the event of an after-hours potential enrollment (i.e., clinic coast time differences), or an immediate need for convenience for the subject, please contact the sponsor PI or Research Project Coordinator.

An electronic copy of the signed and dated consent form for each subject registered from all sites to the protocol is uploaded to the Clinical Trial Management System (CTMS) within 7 days that includes the required demographic information as noted in the UNMC SRC policies and procedures.

Section 5.0 Treatment Plan

The study is an open label, phase II multicenter trial designed to evaluate ruxolitinib as a salvage treatment for subjects with sclerotic GVHD (sclerosis or fasciitis).

5.1 Treatment Schedule and Administration: Ruxolitinib

Drug	Dose/Frequency	Duration	Administration
Ruxolitinib	10 mg BID	6 months, may extend up to 12 months	Oral

Subjects will receive oral ruxolitinib at a dose of 10 mg twice daily. Doses may not exceed 10 mg twice daily. Subjects will record their intake on a medication diary provided to them. Ruxolitinib will be continued for 6 months, unless there is intolerable toxicity, chronic GVHD progression requiring additional systemic treatment or relapse of the underlying malignancy. Subjects with mixed responses or chronic GVHD progression prior to 6 months of therapy that does not require initiation of additional agent are allowed to continue ruxolitinib for the complete 6 month duration. Therapy duration of 6 months will ensure adequate exposure to ruxolitinib, and is important because of the limited options for therapy in the study population and limitations of the current response assessment.

Extended treatment

Subjects who continue to have stable disease, mixed responses or partial/complete responses at the end of 6 months may continue the drug for a total of 12 months. Subjects with chronic GVHD progression (not including stable disease or mixed responses) at the end of 6 months will stop ruxolitinib, regardless of whether or not a new systemic therapy has been added.

Ruxolitinib taper prior to discontinuation

At the end of 6 months, or 12 months for subjects treated on extension study, ruxolitinib will be tapered over a month before discontinuation, for example, a dose reduction by 5 mg every 1-2 weeks. Ruxolitinib may be stopped without a taper in cases of unacceptable toxicities. If an UNMC IRB # 333-18, Protocol Version 1.6 dated 25Jan2021

abrupt cessation of ruxolitinib is required, investigators are strongly encouraged to consider starting or dose-escalating systemic glucocorticoid (prednisone dose ≥ 0.5 mg/kg/day or equivalent dose) for at least a week to avoid rebound symptoms. While coming off ruxolitinib, subjects should be carefully monitored for worsening of GVHD symptoms or any other withdrawal symptoms.

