1.3 Exploratory Objectives

The exploratory objectives are to assess the following:

1. Treatment failure (treatment failure defined as: administration of additional systemic therapy for chronic GVHD, malignancy relapse or mortality) by 6 months from study enrollment
2. Non-relapse mortality by 6 months
3. Change in patient-reported outcomes: skin subscale and summary score of the Lee Chronic GVHD Symptom Scale, and Scleroderma Health Assessment Questionnaire between enrollment and 6 months
4. Response rate in skin/joint and overall at 12 months, for subjects treated on the extension study
5. Proportion who reduce prednisone (or prednisone equivalent) dose by 50% from baseline to 6 months

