5.4 Duration of Study and Follow-up

We estimate that there will be 47 subjects dosed over a 2.5-year period. After accrual is met, we plan to follow the subjects for up to 2 years; the follow-up duration is discussed in detail in the table below.

GVHD response evaluation every 3 months	Therapy duration	End of therapy safety evaluation (30-40 days after the last dose of the study drug)	Last follow-up for GVHD evaluation	Data collection
Stable disease or mixed responses at the end of 6 months	6 to 12 months followed by taper over 1 month ¹	8 months; If therapy continued till 12 months and tapered over the next month, 14 months ²	At the end of 6 months; If therapy continued until 12 months, up to 24 months from the study enrollment ³	Data on survival, relapse of malignancy, subsequent GVHD treatment will be collected till subjects are removed from the study, death or up to a total of 2 years. For subjects who have completed last follow-up for GVHD evaluation, further data may be collected via review of medical records or telephone interview.
Partial/complete responses at the end of 6 months	6 to 12 months followed by taper over 1 month ¹	8 months ⁴ ; If therapy continued till 12 months and tapered over the next month, 14 months ²	Up to 24 months from the study enrollment ³	
GVHD progression, toxicity or relapse ⁵	<6 months (may stop without a taper)	About 30 days after the last dose	At the end of 6 months	

¹If no intolerable toxicity, chronic GVHD requiring initiation of an additional systemic agent, or relapse of underlying malignancy within the 6 months of the study participation, ruxolitinib may be continued till 12 months

²If no toxicity concerns were raised at 12-month follow-up, this evaluation may be performed over the phone with a plan to see the subject in a follow-up at 15 months.

³The subject will be followed every 3 months until progression of chronic GVHD requiring initiation of an additional systemic agent, relapse of underlying malignancy or for a total of 2 years

⁴For subjects with partial or complete responses at 6 months, if no toxicity concerns were raised at 6-month follow-up, this evaluation may be performed over the phone with a plan to see the subject in a follow-up at 9 months.

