5.5.4 End of Month 6 Visit (+/-14 days)

Assessments at the end of month 6 visit will include:

- History and physical exam
- Clinical laboratory parameters (hematology and serum chemistry)
- Comprehensive GVHD assessment including digital pictures of range of motion (if abnormal) and any visible skin lesions, mapping of sclerotic areas (Appendix I)
- Patient reported outcomes
- Research blood collection for correlative studies
- Adverse event monitoring

Data on relapse of the underlying malignancy, survival, chronic GVHD flares, prednisone dose and use of other immunosuppressive agents will be captured at scheduled time points, and verified at each visit.

5.5.5 End of Month 9, 12, 15, 18, 21 and 24 Visit (+/-30 days) (Extended Treatment)

Subjects who maintain complete or partial response at the end of 6 months, OR receive extended therapy (see section 5.4 for details) will be followed every 3 months (+/-30 days) until start of another systemic treatment for chronic GVHD, relapse of underlying malignancy or for a total of 2 years to determine the duration of response.

Assessments at these visits will include:

- History and physical exam
- Clinical laboratory parameters (hematology and serum chemistry)
- Comprehensive GVHD assessment including digital pictures of range of motion (if abnormal) and any visible skin lesions, mapping of sclerotic areas (Appendix I)
- Patient reported outcomes
- Adverse event monitoring if receiving ruxolitinib within the past 30 days

Data on relapse of the underlying malignancy, survival, chronic GVHD flares, prednisone dose and use of other immunosuppressive agents will be captured at scheduled time points, and verified at each visit.

5.5.6 End-of-therapy or Safety Follow-up Visit (30-40 days after the last dose of ruxolitinib)

Subjects will undergo this visit 30-40 days after the last dose of ruxolitinib (see section 5.4 for details).

Assessments at safety follow-up visit will include:

- History and physical examinations
- Clinical laboratory parameters (hematology and serum chemistry)
- Comprehensive GVHD assessment (if a subject withdraws from study treatment prior to 3 or 6 month assessment time points)
- Adverse event monitoring

Subjects with grade 3-4 toxicities are required to undergo close monitoring with repeat testing of any abnormal laboratory or clinical parameter(s) within 2-7 days depending on specific circumstances.

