6.1 Assessment of therapeutic response in chronic GVHD

The established method for response determination in the majority of chronic GVHD therapy trials is clinician-determined response based on organ scoring. The Response Criteria Working Group Report from the 2014 NIH Consensus Conference on chronic GVHD has recommended three general categories of overall response: complete response (CR), partial response (PR), and lack of response (unchanged, mixed response, progression) (1). Further details are provided in the Appendix B and G.

The primary endpoint of this study is to determine the proportion of subjects with complete and partial responses in skin and/or joint, which are defined by 2014 NIH Criteria (1) as follow:

Complete response (CR) in skin and/or joint requires NIH skin and joint score 0, and P-ROM score of 25.

Partial response in skin and/or joint requires decrease in NIH skin score OR joint score by 1 or more points, or increase in P-ROM score by 1 point for any site.

Section 7.0 Study Parameters (also see section 5.5)

Procedures	Baseline (-28 days)	Study Day 1	Treatment			Follow-Up	
			Study Day 14 and 28 (±4 days) ⁷	End of Month 2, 4, 5 (±14 days) ⁷	End of Month 3, 6 (±14 days)	Visits every 3 months (end of month 9, 12, 15, 18, 21, 24) (±30 days)	End of Treatment Safety Follow-Up (30-40 days after last dose)
Informed consent	X						
Eligibility Verification	X						
History and Physical Exam	X				X	X	X
Karnofsky Performance Status	X						
Comprehensive GVHD assessment including digital pictures and body mapping ⁴	X				X	X	X ²
Hematology (CBC)	X		X	X	X	X	X
Serum creatinine, total bilirubin, AST, ALT, Albumin, Alkaline Phosphatase, Calcium, Sodium, Potassium, Blood Urea Nitrogen (BUN), Glucose	X		X	X	X	X	X
Total Cholesterol, LDL, HDL, Triglycerides	X			X (check at the end of 2 months+/-14 days, then as clinically indicated)			
Amylase, lipase	X			Check if triglyceride level ≥500 mg/dl			
Urine Pregnancy	X						
Hepatitis B Surface Antigen ¹	X						
Hepatitis C antibody ¹	X						
CMV DNA		Monthly for the first 3 months and as clinically indicated					
HIV testing ¹	X						
Electrocardiogram	X						
Other Laboratory tests		As clinically indicated					
Radiology Tests		As clinically indicated					
Patient Reported Outcomes Lee Chronic GVHD Symptom Scale Scleroderma Health Assessment Questionnaire	X				X	X	
Correlative study samples ³	X				X		
Ruxolitinib		X	X	X	X	X ⁸	
Adverse event monitoring		Monitor until 30 days after treatment					

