Concomitant medications including systemic glucocorticoid ⁵	X				X	X ⁶	X ⁶

1. Testing for Hepatitis B, C and HIV completed prior to transplant will be acceptable. No additional testing is required for study eligibility.
2. If a subject withdraws from study treatment prior to the end of 3 or 6 month assessment time points, the comprehensive GVHD assessment should be completed at the End of Treatment/Safety follow up visit.
3. The correlative sample can be collected at any time during the scheduled visit.
4. Body mapping and digital pictures will be uploaded in the eCRF. The instructions are listed the CRF Completion Guidelines
5. For all subjects enrolled in this study including those enrolled in the past, data on only concomitant medications of interest (i.e. glucocorticoid, and other immunosuppressive agents including narrow band UVB phototherapy and extracorporeal photopheresis) should be collected at baseline, at each 3-monthly visit until the subject stops ruxolitinib and end of treatment/safety follow-up.
6. After the subjects stop ruxolitinib, if a new immunosuppressive agent is started for treatment of GVHD, only data on the new immunosuppressive medicine should be collected.
7. The subject should be called to check on dose compliance and lab results.
8. If the subject has stable disease, mixed responses or partial/complete response, the subject can continue to take ruxolitinib for a total of 12 months before tapering off the study drug. Please review section 5.1 for further details.

Section 8.0 Drug Formulation and Procurement

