10.2.1 Efficacy Endpoints

Primary and secondary objectives

The primary objective of the study is to determine the complete and partial responses in skin and/or joint after 6 months of therapy. The response rate will be reported as a proportion and 95% exact confidence interval. This analysis will be conducted on the full analysis set.

The secondary objective is to determine the overall complete and partial responses after 6 months of therapy. The response rate will be reported as a proportion and 95% exact confidence interval.

Exploratory Objectives

Treatment failure (treatment failure defined as: administration of additional systemic therapy for chronic GVHD, malignancy relapse or mortality) by 6 months from study enrollment.

Time to treatment failure will be defined as study enrollment to failure event. Kaplan-Meier methods will be used to estimate the distribution for time to treatment failure. The failure rate at 6 months will be estimated from the Kaplan-Meier curve, and the rate and 95% confidence interval will be reported.

Time to non-relapse mortality will be computed as study enrollment to non-relapse death. Cumulative incidence methods will be used to estimate the distribution with relapses and relapse related deaths as competing events. The rate at 6 months will be estimated from the curve along with 95% confidence intervals.

For subjects treated on the extension study, the response rate at 12 months will be reported as a proportion and 95% exact confidence interval.

For subjects on steroids at baseline, we will explore the change in dose of steroids at 6 months. We will calculate the average percent change in dose for each subject along with a 95% CI. We will also determine the number and proportion of subjects that had a dose reduction greater than 50% as well as an exact 95% confidence interval.

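### For extension subjects the taper starts at the end of month 12 but the month-12 visit may come up to 30 days later, so the exploratory 12-month response can be scored at a reduced dose

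*Combined protocol and SAP*

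**What the plan says.** Three places put the planned taper after 12 months of drug for extension subjects.

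- Section 5.1, on tapering: "At the end of 6 months, or 12 months for subjects treated on extension study, ruxolitinib will be tapered over a month before discontinuation".
- Section 5.4, in the table, times the end-of-therapy safety evaluation: "If therapy continued till 12 months and tapered over the next month, 14 months".
- Section 7.0, footnote 8, for subjects with stable disease, a mixed response, or a partial or complete response: "the subject can continue to take ruxolitinib for a total of 12 months before tapering off the study drug".

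The month-12 visit has a two-sided window. The section heading reads "5.5.5 End of Month 9, 12, 15, 18, 21 and 24 Visit (+/-30 days", and the Section 7.0 table has the same column: "Visits every 3 months (end of month 9, 12, 15, 18, 21, 24". This visit includes the comprehensive GVHD assessment and the patient-reported outcomes.

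The visit feeds an exploratory objective in Section 1.3: "Response rate in skin/joint and overall at 12 months, for subjects treated on the extension study". Section 10.2.1 gives the analysis: "For subjects treated on the extension study, the response rate at 12 months will be reported as a proportion", with an exact 95% confidence interval. Neither section sets a condition on dose or taper status at the assessment.

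**The concern.** The taper has a calendar start and the visit has a window that runs past that start. A site can follow both rules and still examine an extension subject part-way through withdrawal. Section 5.1 itself expects a possible signal in that period: "While coming off ruxolitinib, subjects should be carefully monitored for worsening of GVHD symptoms or any other withdrawal symptoms".

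At stake is what the 12-month proportion describes. It is presented as response on extended treatment, but as written it can mix subjects still on their treatment dose with subjects being withdrawn. If withdrawal worsens GVHD, the mix lowers the observed response and worsens the patient-reported scores. The assessment is also hard to replace. Section 5.4 footnote 2 lets the 14-month safety contact be made by phone, with the next visit at 15 months, when a tapered subject is off drug.

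**Working it through.** **Inputs**

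- Full dose: 10 mg twice daily, or 20 mg/day (Section 5.1).
- Taper: starts at the end of month 12 and lasts about a month. The example step is 5 mg every 1-2 weeks (Section 5.1).
- Safety evaluation: 30-40 days after last dose, stated as 14 months for these subjects (Section 5.4).
- Month-12 window: +/-30 days (Section 5.5.5 and Section 7.0).
- Baseline: up to 28 days before treatment (Section 5.5.1). Enrollment is the consent date (Section 4.2).

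**Step 1. Reproduce the plan's own date.** With 30.4 days per month, 12 months of drug + 1 month of taper + 30 to 40 days = 12 + 1 + (0.99 to 1.32) = 14.0 to 14.3 months. This matches the stated 14 months. A taper inside the 12 months would give 12 + (0.99 to 1.32) = 13.0 to 13.3, which does not match. The taper therefore runs after month 12.

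**Step 2. How late the visit can be relative to the taper start.** Let g be the days from the date at which visit months start to the first dose. The latest in-window visit falls 30 - g days after 12 months of drug.

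- Months counted from first dose: g = 0, so 30 days.
- Months counted from consent, at the longest gap: g = 28, so 30 - 28 = 2 days.

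The month-12 anchor is not stated. Section 5.5 counts month 3 from starting ruxolitinib and month 6 as months of therapy, which favors first dose. Section 5.4 counts the 24-month GVHD follow-up from enrollment.

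**Step 3. Dose at a late visit, as illustration.** I assume 5 mg steps in total daily dose from 20 mg/day, with two schedules that reach zero in about the planned month. Day 0 is the end of month 12.

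| Day | 7-day steps, first cut day 7 | 10-day steps, first cut day 0 |
|---|---|---|
| 0 | 20 mg/day | 15 mg/day |
| 7 | 15 | 15 |
| 14 | 10 | 10 |
| 21 | 5 | 5 |
| 28 | 0 | 5 |
| 30 | 0 | 0 |

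Under either schedule, a visit two weeks late finds the subject at half dose and a visit at day +30 finds the subject off drug. Days off drug inside the window are 3 (days 28, 29 and 30) in the first schedule and 1 (day 30) in the second. With g = 28, the latest visit (day +2) finds 20 or 15 mg/day.

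**Step 4. Scale of one misread response.** The number extending is not given. At the upper limit of all 47 dosed subjects, one subject moves the proportion by 1/47 = 2.1 points. With an assumed 20 extending, the move is 1/20 = 5.0 points. For illustrative counts the exact 95% intervals are:

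- 21/47 = 44.7% (30.2 to 59.9), width 59.9 - 30.2 = 29.7 points.
- 9/20 = 45.0% (23.1 to 68.5), width 68.5 - 23.1 = 45.4 points.

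The expected bias would be the share of extension subjects seen after the first cut, times the chance that a few weeks at lower dose reverses a response. The documents give neither.

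**The case against.** The strongest reply is that ordinary practice closes the gap. The visit and the taper share one nominal time. The taper steps are only an example, so staff must set them for each subject, and drug and diary come to each visit. Many sites will therefore start the taper at the visit. The endpoint is exploratory and descriptive, and the Introduction says sclerotic responses are slow. The diary makes mid-taper assessments identifiable. The 12-month response is nowhere defined as a full-dose response, and reduced doses for toxicity or interacting drugs are allowed throughout.

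Most of this stands, and it limits the size. None of it sets the order of the two events. Dose cuts for toxicity or interactions are part of treatment, whereas a planned withdrawal is its end.

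Two stronger readings are tempting. First, a reader might infer that about half the 12-month assessments are affected, since 30 of the 61 window days (49%) fall after day 0. That is a share of calendar days, not of visits, and it assumes that months count from first dose.

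Second, a reader might infer that the primary 6-month endpoint has the same fault. Section 5.1 makes extension depend on GVHD status at the end of 6 months, so the assessment normally comes before any taper, and that window is only +/-14 days. What remains is a subject who does not extend, tapers by the calendar and is seen late. That is too thin to support a claim against the primary endpoint.

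**Conclusion.** The point holds for month 12 in extension subjects. The stated rules together allow a compliant site to score the 12-month response and patient-reported outcomes after the taper has begun. Any bias would be against the drug.

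The size cannot be derived and is probably small. The possible late exposure runs from about 2 days (months counted from consent, 28 days before first dose) to 30 days (months counted from first dose). The doses tabulated above rest on my assumed schedules. The ordering gap itself rests on no assumption beyond the text. The primary endpoint and the two-stage decision are not affected. This is a cheap improvement to an exploratory endpoint.

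**What to change.** In Sections 5.1, 5.5.5 and 7.0, require the month-12 GVHD and patient-reported assessment to be done on or before the day of the first planned taper step, with a window of -30/0 days for subjects still on drug. Tying the visit to the taper step makes the order hold whichever date the months are counted from. If a subject is still seen late, keep and count the assessment and record the dose on that day from the diary. Leave the month-6 window unchanged: extension is decided on the findings of that visit, so a window that depended on extension could not be known beforehand and would alter the primary assessment for little gain.

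The change is to schedule wording only. It needs no extra drug or visit, and sample size, alpha, power and the 14-month safety date stand. The cost is less scheduling flexibility at one visit, whose window shrinks from 61 to 31 days. Some assessments will also fall slightly before 12 months, which the present window already allows.
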